1. SYNOPSIS

Study Title	Operational evaluation of Mass Screening and Treatment using ultrasensitive rapid detection tests to reduce P. falciparum malaria incidence and prevalence in a malaria elimination program in Eastern Kayin State, Myanmar.	
Internal ref. no.	MAL 17011	
Study Design	Stepped wedge intervention	
Study Participants	Populations of villages with high P. falciparum incidence located in Eastern Kayin State, Myanmar.	
Planned Sample Size	60 villages (group 1) 60 villages (group 2)	
Planned Study Period	3 years	
	Objectives	Outcome Measures
Primary	To measure the impact of URDT-based MSAT on P. falciparum incidence at village-level (group 1 & 2)	Adjusted incidence rate ratio before/after MSAT
Secondary	1) To measure the impact of MSAT on prevalence of P. falciparum infection in malaria hotspots (group 1)	1) Prevalence of P. falciparum infection measured in the village by URDT and by reference method
	2) To measure the impact of reactive MSAT on incidence of seasonal malaria peaks / outbreaks (group 2)	2) Change in the incidence dynamics over the transmission season
	3) Feasibility of MSAT as a programmatic tool and as a reactive strategy (group 1 and 2)	3) Coverage of village population with intervention
	4) % of infections treated compared to infections detected by reference method (group 1 only)	4) % of P. falciparum positive samples by reference method which were positive by URDT and treated; % of P. falciparum negative samples by reference method which were positive by URDT and treated

2. ABBREVIATIONS

ACT	Artemisinin Combination Therapy
AL	Artemether Lumefantrin
CE	Community engagement
DP	Dihydroartemisin-Piperaquin
ELISA	Enzyme Linked Immuno Sorbent Assay
GCP	Good Clinical Practice
GMS	Greater Mekong Subregion
HRP2	Histidin Rich Protein 2 (Plasmodial antigen detected by lateral flow assays: RDT or URDT)
ICF	Informed Consent Form
MDA	Mass drug administration
METF	Malaria Elimination Task Force
MP	Malaria Post
MSAT	Mass Screening and Treatment
NMCP	National Malaria Control Program
OxTREC	Oxford Tropical Research Ethics Committee
PI	Principal Investigator
PIS	Participant Information Sheet
PMQ	Primaquine
Q7C7	Quinine 7 days; Clindamycine 7 days
RDT	Rapid Diagnostic Test
sld PMQ	single low dose Primaquine
SOP	Standard Operating Procedure
uPCR	Ultrasensitive quantitative polymerase chain reaction
URDT	Ultrasensitive Rapid Diagnostic Test

3. BACKGROUND AND RATIONALE

Malaria elimination has been undertaken in the Western Greater Mekong Subregion (Western Thailand, Eastern Myanmar) in an attempt to prevent the spread of artemisinin- and multidrug resistant falciparum parasites.

The malaria elimination task force (METF) has been operating in Eastern Kayin State since April 2014. METF is present in the four townships of Hapun, Hlaingbwe, Myawaddy and Kawkareik, in a total of 158 village tracts. METF is providing access to early diagnosis and treatment of malaria in 1200 villages through community-based facilities “Malaria Posts” (MP) [1]. The monitoring of falciparum malaria incidence in the villages after the opening of a MP showed that incidence decreases quickly in most locations (approximately by 25% per quarter of MP activity, Figure 1A). As a result in April 2017 a total of 965 villages out of 1,222 villages (79%) corresponding to 104 village tracts were free of *P. falciparum* malaria for at least 6 months.

However the activity of the MP had more limited impact in villages with high prevalence of asymptomatic infections: a slower or no decrease of falciparum was observed, even after >24 months of MP activity (Figure 1B).

[figure not shown]

Figure 1: Malaria incidence (falciparum in red and vivax in black) since MP opening in the townships of Hapun (n=468 MP) and Myawaddy (n=100) where hotspots were identified (52/69 located in Hapun Township, 7/69 in Myawaddy). Different y-scales are used in each graph.

A: non-hotspot villages. The widening confidence intervals after 24 months indicate that fewer MP have been active for 2 years or more. The oscillations in *P. vivax* incidence are related to seasonal peaks occurring in the same locations in Myawaddy Township.

B: hotspot villages, without intervention. Only 16 hotspots contribute to follow-up for durations of MP activity above 18 months. These high incidence locations were only identified during the final campaign of baseline surveys (Nov. 2016 to Jan. 2017) and had not been addressed by April 2017. The median duration of MP activity before intervention was 12 months (IQR=5-16). Over the period corresponding to a duration of MP activity between 0 and 18 months, a decrease can be observed in hotspots which is captured by the statistical model.

Following a successful pilot study initiated in 4 villages in 2013 [2], METF has conducted surveys to measure the prevalence of asymptomatic malaria infections. Villages with high prevalence of malaria (>40%) in which falciparum represented at least 20% of malaria infections, were defined as hotspots and treated with a 3-month mass drug administration campaign. These campaigns were very successful at depleting the reservoir of asymptomatic carriage of *P. falciparum* (Figure 2), which translated in a significant decrease in clinical episode incidence (Figure 3). In spite of its success, this strategy is difficult to scale up due to numerous constraints and was not considered by the Myanmar NMCP. However, the successful decrease in case incidence obtained by treating the reservoir of asymptomatic carriers sparks interest for a simpler and faster intervention, relying on mass screening and treatment (MSAT) rather than MDA (Table 1). Such approach was previously impossible due to the lack of sensitivity of standard RDT to detect asymptomatic infections. A newly available ultrasensitive RDT (URDT) shows a 50% sensitivity and 99% specificity compared to uPCR. This sensitivity is sufficiently high to allow accurate detection of high prevalence villages, and to warrant evaluation of the impact of a URDT-based screening and treatment intervention. MSAT is a method approved by the Myanmar NMCP and recommended by the WHO.

[figure not shown]

Figure 2: Impact of MDA on *P. falciparum* prevalence (95% confidence interval) comparing baseline and 12 months after MDA (n=40 villages) in villages equipped with MP and addressed with MDA between January 2015 and April 2016.

By design, an MSAT intervention using a field test will not identify all carriers. However, it is likely to decrease village level prevalence by 50%, and parasite biomass by >97%, since 87% of infections with parasite densities >1000 parasite/mL are expected to be identified. This depletion of the reservoir could be sufficient to durably modify the village-level transmission and initiate or accelerate the MP-driven decrease. Additionally, a URDT-based MSAT strategy could be an extremely useful tool to respond to malaria outbreaks. Indeed, by rapidly screening the population of a village where the incidence has reached alarm thresholds, parasite carriers could be rapidly identified and treated, leading to a rapid decrease in the reservoir and an interruption of the transmission.

[figure not shown]

Figure 3: Average *P. falciparum* and *P. vivax* incidence in hotspots before and after MDA, centered on date of MDA. A marked decrease in *P. falciparum* incidence after MDA can be observed, in spite of an increase in incidence around 15 months after MDA. This increase is related to 5 hotspots (out of 52 followed up to M18) showing an incidence above 50 case/1000 for 1 month during the second year after MDA. This increase did not persist further.

In this project, we aim at an operational research deployment of URDT-based MSAT in the METF elimination program. This intervention will be tested in two types of setting, which correspond to two arms in this study. In group 1, MSAT will be used in a programmatic setting in order to decrease the reservoir of asymptomatic carriers in high incidence villages (following the same principles and objective as previously deployed MDA interventions). In group 2, we take advantage of the lighter framework of MSAT to use it as a reactive intervention in order to respond to malaria outbreaks in low to intermediate incidence villages. The MSAT intervention will be preceded with community-level consent and community engagement (CE) activities. MSAT will be conducted over a period of approximately 1 week in each hamlet, village or group of villages, and will consist in administering a *P. falciparum* URDT to all individuals agreeing to participate. A limited subgroup (expected 5-25%) will be found positive and receive supervised treatment over 3 days for the standard regimen (DP to cure asexual stage infection + single low-dose primaquine to destroy gametocytes). After this intervention, the incidence of clinical falciparum episodes will be monitored by the village MP. In group 1, a comparison of the prevalence at baseline and 12 months after MSAT intervention will be performed through a second URDT survey, in addition to which both baseline and 12-month surveys will include the collection of a 50 μ L capillary blood sample for reference detection in the laboratory.

The intervention will be evaluated primarily on its ability to reduce yearly cumulative incidence of clinical falciparum malaria compared to year before intervention. Additional evaluations of the impact of MSAT will include: in group 1, comparison of asymptomatic infection prevalence; and in group 2, modifications of the shape of the incidence curve following intervention.

Potential risks and benefits for participants

This study has limited risks for participants. 75 to 95% of participants will only undergo a malaria rapid diagnostic test (URDT) requiring a finger prick and receive a negative result. 5 to 25% of participants are expected to be found URDT positive. The specificity of the test is high compared to uPCR (99%) as well as predictive positive value (88%), ensuring that >9/10 of these positive individuals will be infected with *P. falciparum* and will benefit from the ACT treatment ([3], Appendix D). The safety of DP and single low dose primaquine are well-described, including among asymptomatic individuals [2,4]. The risk associated with treatment will be limited. All screening participants in group 1 will also be sampled for 50 μ L capillary blood using the same finger prick as used for the URDT, which does not aggravate the risk. All procedures on participants will be conducted by trained medical personal.

Participants will benefit from this study by acquiring knowledge of their infection status as individuals and as a community. Infected individuals will be treated, which will decrease the potential negative consequences of a long-lasting infection [5,6] without increasing the risk of a subsequent clinical episode [7]. Households where positive participants will be identified will receive additional guidance on measures to protect against vectors and be reminded to consult the village MP within 24h in case of fever onset. At the community level, treatment of asymptomatic carriers is expected in reducing significantly the number of infective individuals, thus limiting the infection of mosquitoes and decreasing the overall village transmission and malaria burden.

Interest of the research

The METF target area in Eastern Kayin State, Myanmar, is piloting strategies with potential applications for >20 countries in the 2020 horizon, and many more countries by 2030 since elimination is one of the Sustainable Development Goals. It is also a region of significant artemisinin resistance, and under the threat of the expansion of a multidrug resistant falciparum lineage spreading in the GMS. Strategies developed and tested in a context of antimalarial resistance are therefore extremely valuable for this region.

4. OBJECTIVES AND OUTCOME MEASURES

Objectives	Outcome Measures	Timepoint(s) of evaluation of this outcome measure (if applicable)
Primary Objective To measure the impact of URDT-based MSAT on P. falciparum incidence at village-level.	Adjusted incidence rate ratio before/after MSAT	Follow-up from MP opening to end of study
Secondary Objectives 1) To measure the impact of MSAT on prevalence of P. falciparum infection in malaria hotspots	1) Prevalence of P. falciparum infection measured in the village by URDT and by reference method (group 1)	1) Comparison between M0 survey (during MSAT) and M12 survey (12 months after)
2) To measure the impact of reactive MSAT on incidence of seasonal malaria peaks / outbreaks.	2) Change in the incidence dynamics over the transmission season (group 2)	2) Duration and height of seasonal peak before, during and after reactive intervention
3) Feasibility of MSAT as a programmatic tool and as a reactive strategy.	3) Coverage of village population with intervention	3) coverage based on census conducted before/during MSAT
4) % of infections treated compared to infections detected by reference method	4) % of P. falciparum positive samples by reference method which were positive by URDT and treated; % of P. falciparum negative samples by reference method which were positive by URDT and treated (group 1)	Group 1 only
Tertiary Objectives Retrospective comparison of MSAT versus MDA on prevalence and incidence of P. falciparum malaria	Cumulative incidence of falciparum malaria episodes before and after MDA/MSAT; prevalence of falciparum infection before and after MDA/MSAT	Entire incidence series

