5. STUDY DESIGN

Stepped-wedge open-label, non-randomized, cluster intervention.

This study will be performed in clusters (hamlet (isolated group of household, village, or group of village). The intervention will be conducted in two types of clusters, both corresponding to locations where an excess of case was detected.

Group 1: Sustained high incidence clusters, characterized by a yearly cumulative incidence >84 cases/1000/year

Villages in group 1 will be attributed an intervention a given year based on the cumulative incidence over the previous 12 months (METF stratification January, including the last 2 transmission seasons). The order of intervention will be decided based on logistic constraints and highest incidence.

Group 2: Focal transmission clusters, corresponding to locations where an epidemic alert has been signalled and confirmed (see definition of thresholds).

*Villages in group 2 will be attributed an intervention based on *P. falciparum* incidence in the previous 4 weeks. In near-0 transmission area, an intervention will be conducted in each likely source location of transmission of a locally acquired case. In the other areas (METF1+METF2), the intervention will be triggered when the incidence is above the pre-defined epidemic threshold.*

In each cluster, all inhabitants will be invited to undergo an URDT test to identify their infection status, and will receive the appropriate treatment according to their characteristics. Information on village inhabitants absent during the MSAT activities will be obtained from village population lists provided by the village headman and from household member declarations. During the URDT screening, all individuals will receive a unique identifying number that will be used to record demographic data in the MSAT paper logbook and to label URDT and reference sample.

Before and after MSAT intervention, incidence of clinical malaria episodes will be recorded at the MP (1 or several) serving the cluster receiving the intervention. No individual data will be collected to link clinical case participation, infection status and incidence of clinical episodes.

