6. PARTICIPANT IDENTIFICATION AND RECRUITMENT

6.1. Study villages selection

The study village selection is based on the definition of three main strata of *P. falciparum* incidence corresponding to different probabilities of rapid elimination. Based on 2017 data, the townships of Myawaddy, Hlaingbwe and Kawkareik have almost interrupted *P. falciparum* transmission (95% of villages with 0 incidence), while heterogeneity persists in Hpapun township with diverse transmission and incidence profiles.

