6.1.2. Group 2: seasonal focal transmission villages/locations

This group will follow the NMCP case/and foci investigation guidelines, but use URDT instead of standard RDT for screening. MSAT group 2 locations will be cluster of houses, villages or clusters of villages selected based on the results of case or foci/outbreak investigation.

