6.1.2.1 Village inclusion after case investigation

Case investigation will be performed systematically in the three townships of Myawaddy, Kawkareik and Hlaingbwe, upon notification of ≥ 1 *P. falciparum* clinical case. The aim will be to determine the most likely location of transmission.

The village or cluster of houses corresponding to the most likely location of transmission will be included in group 2 if it is located in Myawaddy, Kawkareik and Hlaingbwe.

The most likely location of transmission will not be included in group 2 if it is located outside METF area, or in Hpapun township.

However, upon evolution of the overall incidence, subdivisions of Hpapun township reaching 0-transmission will be included in the case investigation activities and therefore eligible for case investigation and inclusion in group 2 MSAT.

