6.1.2.2 Village inclusion after outbreak investigation

Outbreak alarms will be generated from Hpapun township by the analysis of weekly *P. falciparum* incidence data by METF surveillance system (e.g. following thresholds such as cases >90th percentile at the village or cluster level). An investigation will be conducted to determine the context of transmission and assess the contribution of imported case in this increase.

The cluster will be included in group 2 if the investigation concludes to the existence of a local increased transmission episode.

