9.2. The Number of Participants (group 1 only)

The sample size can be calculated for group 1 only, since the baseline cumulative incidence in group 2 will depend on surveillance outcomes, and often correspond to responses to a single case.

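### The group 2 seasonal-peak outcome has no meaning in single-case clusters, and in outbreak clusters peak height is partly determined before MSAT, to an unstated extent

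*Combined protocol and SAP*

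**What the plan says.** Section 4 gives secondary objective 2 as the effect of reactive MSAT on seasonal peaks and outbreaks. The outcome is a change in incidence dynamics over the season, labelled group 2 with no subset named, and it is evaluated by "Duration and height of seasonal peak before, during and after reactive intervention".

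Group 2 is filled by two routes.

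- **Case investigation (sections 5 and 6.1.2.1).** "In near-0 transmission area, an intervention will be conducted in each likely source location of transmission of a locally acquired case". Investigation starts at one or more notified cases in three townships that section 6.1 describes as having "95% of villages with 0 incidence". The unit included is the presumed source: "The aim will be to determine the most likely location of transmission". Under section 6.1.2 a unit can be as small as a group of houses: "MSAT group 2 locations will be cluster of houses, villages or clusters of villages". Section 9.2 says the group 2 baseline will "often correspond to responses to a single case".
- **Outbreak investigation (sections 5 and 6.1.2.2).** In the other areas "the intervention will be triggered when the incidence is above the pre-defined epidemic threshold". The threshold is given by example only: "following thresholds such as cases >90th percentile at the village or cluster level". An investigation must then confirm a local increase. Section 7.1 adds meetings with authorities and with the population, agreement, and the setting of a date. Section 3 puts the MSAT itself at about one week.

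No time from alarm to MSAT is stated. Section 4 does not define the peak, its start and end, or the season it is compared with. Section 9.3 describes a secondary analysis for prevalence only.

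**The concern.** A peak needs a rise and a fall. A cluster admitted on one case has neither, so its height and duration describe the admission rule and not MSAT. Pooled with outbreak clusters, these units add changes from 1 to 0 that look like success and would often occur with no intervention.

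Outbreak clusters have a different problem. MSAT is triggered by the rise and arrives some weeks into it, so part of the height is in place before MSAT can act. Selection on a high count also makes later counts tend to be lower. The first feature can hide a real effect on height; the second can create an apparent one. Both bear on what may be claimed for reactive MSAT.

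**Working it through.** The documents give no sample size, effect or delay for this outcome, so there is no stated figure to reproduce. The checks below are illustrations on stated assumptions.

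**1. Single-case clusters.** Inputs: 190 inhabitants (section 9.2.1, a group 1 figure, borrowed); 1 to 10 cases/1000/year (assumed); independent Poisson cases.

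- One case is 1/190 = 5.3 per 1000, with an exact 95% interval of 0.13 to 29.3 per 1000.
- The yearly mean is a = rate × 190/1000, that is 0.19 at 1/1000 and 1.9 at 10/1000. The weekly mean is a/52.
- P(some week has ≥2 cases, given ≥1 case in the year) = [1 − P(week ≤1)^52] / [1 − exp(−a)]. This is 0.2% at 1/1000, 1.4% at 5/1000 and 3.9% at 10/1000. Height is almost always 1.
- P(no case in the next 12 months with no MSAT effect) = exp(−a). This is exp(−0.19) = 83%, exp(−0.95) = 39% and exp(−1.9) = 15% at 1, 5 and 10/1000.

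Because the unit is the presumed source, the index case may also be missing from that unit's own malaria post series.

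**2. When the alarm comes.** Take the example threshold as a village's own 90th percentile: 0.10 × 52 = 5.2 weeks a year above it. With two seasons (section 5) and symmetric peaks that is 2.6 weeks per peak, so a usual-size peak crosses b = 1.3 weeks before its maximum (2.6 weeks with one season). For a Gaussian peak k times the usual size, crossing comes t = √(b² + 2·SD²·ln k) weeks before the maximum.

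| Size and seasons | SD 2 weeks | SD 3 weeks | SD 4 weeks |
|---|---|---|---|
| k = 2, two seasons | 2.7 | 3.8 | 4.9 |
| k = 2, one season | 3.5 | 4.4 | 5.4 |
| k = 3, two seasons | 3.2 | 4.6 | 6.1 |

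If alarm to end of MSAT took 4 weeks (assumed), MSAT would end after the maximum in some cells and up to about two weeks before it in others.

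**3. How much of the height is already in place.** Assumptions: Poisson simulation of a bell-shaped outbreak with SD 2 to 6 weeks, background 0.1 case/week, alarm at the first week with ≥2 cases, MSAT acting 2 to 4 weeks later and halving later cases.

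| Outbreak size | Untreated maximum already reached | Fall in mean peak height |
|---|---|---|
| 5 cases | 90–96% | 1.5–4.2% |
| 10 cases | 66–88% | 4.3–13.5% |
| 20 cases | 29–76% | 8.3–26.1% |
| 40 cases | 6–58% | 13.5–36.3% |

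With an 8-week delay the maximum has been reached in 93–98% of 10-case and 49–97% of 40-case outbreaks.

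**4. Selection on a high count.** Take a flat rate, no MSAT effect, and a trigger at ≥2 cases in a week (≥3 at 1.0 case/week). The highest week in the 26 weeks after the trigger, divided by the highest in the 26 weeks up to and including it, is 0.51, 0.80, 0.96 and 0.96 at 0.1, 0.3, 0.5 and 1.0 case/week. The group 1 cut-off of 84/1000/year is 84 × 190/1000/52 = 0.31 case/week in a village of 190, so the first two ratios are nearest to group 2 villages of that size.

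**The case against.** The strongest reply concerns outbreak clusters. A reader might infer that peak height there is largely fixed before MSAT can act. The documents do not support that. They give no delay, the percentile is only an example, and section 3 envisages rapid screening once an alarm threshold is reached. The third check shows that larger outbreaks with a short delay leave real room for height to respond, and the second shows that MSAT can finish before the maximum. This objection stands: only direction can be claimed, not degree.

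Nor do the documents show that objective 2 is unanswerable. The outcome is worded as a change in dynamics, and section 3 speaks of the curve's shape after intervention. Duration can respond even where height cannot. The timing entry can be read as the seasons before, of and after MSAT, in which case next-season height is not fixed in advance. Under that reading the early part of the problem goes, but selection on a high count remains. The primary outcome also covers group 2 incidence (section 1), so this is not the only evidence on reactive MSAT.

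It can also be said that one case is not a seasonal peak, so the objective excludes such clusters by its own terms. That is the sensible intention, but section 4 labels the outcome group 2 without restriction. How many clusters are affected is unknown; section 9.2 gives no share.

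**Conclusion.** The point holds in two parts of different strength.

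For single-case clusters it is firm and follows from the protocol's own text. The figures (0.2% to 3.9% for any week with two or more cases) rest on the borrowed village size, the assumed rates and independent cases; clustered cases would raise them.

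For outbreak clusters it holds in direction. Height is partly determined before MSAT, and entry on a high count biases before/after comparisons towards a fall. The extent depends on delay, outbreak size and spread, none of which the documents state.

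The change is worth making, but it concerns one secondary outcome with no power calculation and does not touch the primary analysis. Section 9.1 breaks off mid-sentence in the text available, so nothing here rests on what it omits.

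**What to change.** In section 4, with matching text in section 9.3:

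1. Limit the peak outcome to clusters entering by section 6.1.2.2. Report section 6.1.2.1 clusters separately and descriptively, for example by further locally acquired cases within 12 months, with no claim of effect.
2. State the alarm threshold used in the analysis as a number. In a village of 190 at 20/1000/year or less, the Poisson 90th percentile of weekly counts is 0, so one case would exceed it and the single-case problem would return.
3. Report the time from alarm to MSAT for each outbreak cluster, and treat peak height as descriptive.
4. Use two measures: weeks from the alarm until cases are back below the threshold, and cases per 1000 from MSAT to season end. Duration should not start at MSAT completion: in the second check a usual-size peak with two seasons is above threshold for only 2.6 weeks, so after a 4-week delay that time would be zero whatever MSAT did.
5. Compare with alarms found by applying the same threshold to existing weekly malaria post data from periods or villages without MSAT, aligned on the alarm date, instead of with the same cluster's earlier seasons. For the second measure, start the comparator count at the same number of weeks after the alarm. Allow for season and for duration of malaria post activity, since section 3 reports a fall of about 25% per quarter in most villages.

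Cost: smaller subsets and some extra analysis of data already collected. One limit remains: untreated alarms may not have been investigated for imported cases, so the comparison will be supportive and not conclusive.

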9.2.3. Sample size for retrospective incidence comparison between MSAT and MDA

If comparing 50 MSAT villages and 50 MDA, we will be able to differentiate MSAT from MDA efficacy if MSAT achieves around 50% of MDA impact on incidence or less.

The average village size was 190 inhabitants (coefficient of size variation=0.64) with an intra-cluster correlation coefficient of 0.12 (estimated using incidence series) and MDA was already completed in 60 villages. The 10 villages in which MDA was conducted based on prevalence values that will be the furthest

from what will be measured during the MSAT campaign will be excluded. Villages receiving MSAT after MDA will be excluded from MSAT group. With a comparison of 50 MSAT, it will be possible to detect a difference in incidence rate of 50/1000/year between the two groups (with alpha=5% and power=80%). This would correspond to a reduction of incidence by only 40% after MSAT (70 cases/1000/year after compared to 125 before). With MDA, 80% incidence reduction was achieved: the average cumulative incidence during the first year after MDA was 20 case/1000/year, compared to 125 before.

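### The tertiary MSAT-versus-MDA incidence comparison has no common post-intervention window: section 4 takes the whole series, 9.2.3 is sized on first-year MDA incidence, and 9.3 gives no analysis.

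*Combined protocol and SAP*

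**What the plan says.** Section 4 lists, as a tertiary objective, a retrospective comparison of MSAT with MDA. Its incidence outcome is "Cumulative incidence of falciparum malaria episodes before and after MDA/MSAT", and the time point is "Entire incidence series". No common length of follow-up is given for the two groups.

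Section 9.2.3 sizes this comparison for 50 MSAT and 50 MDA villages, with a detectable difference of 50/1000/year at alpha 5% and power 80%. The MDA input is that "the average cumulative incidence during the first year after MDA was 20 case/1000/year, compared to 125 before". The MSAT input is "70 cases/1000/year after compared to 125 before", with no window named.

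Section 9.3 uses 12 months before and 12 months after MSAT for the primary outcome. Its only comparison with MDA concerns the fractional change in prevalence.

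On follow-up, the Figure 2 legend in section 3 describes 40 villages "addressed with MDA between January 2015 and April 2016". Section 6.1.1 places the first MSAT wave in the first semester of 2018. Section 7.9 ends follow-up at 12 months when URDT prevalence is below 5% and the upper confidence limit is below 10%. At 5% or more a further MSAT round is triggered, and follow-up runs to 12 months after the last MSAT or 36 months after the first.

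**The concern.** A before/after rate compared between two groups has a clear meaning only if both are observed over the same time since intervention. Here the MDA villages were treated two to three years before MSAT starts, so their series are much longer. Dividing by person-time removes the effect of length itself. It does not remove the effect of what happens in the later years.

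Three things can then enter the contrast that are not differences between MSAT and MDA:

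- **Time since intervention.** The MDA rate would describe several years, the MSAT rate mainly the first one to three.
- **Late changes after MDA.** The Figure 3 legend reports a rise around month 15, driven by 5 of 52 hotspots "showing an incidence above 50 case/1000 for 1 month during the second year after MDA". A first-year window leaves it out and the whole series takes it in.
- **Outcome-dependent follow-up.** Under 7.9 the MSAT villages with higher M12 prevalence stay longer and are treated again. A whole-series MSAT rate gives them more weight and includes the effect of the second round.

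The comparison is retrospective and not randomised, and an open window also leaves room to choose it after the results are seen.

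**Working it through.** **1. The plan's own figure.** Inputs from 9.2.3: 50 villages per group, 190 inhabitants per village, coefficient of variation of size 0.64, intra-cluster correlation 0.12, rates 70 and 20 per 1000/year. Assumptions: one person-year per inhabitant, a two-sided test, Poisson variance.

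- Design effect = 1 + ((0.64² + 1) × 190 − 1) × 0.12 = 33.0
- Effective number per group = 50 × 190 / 33.0 = 288
- Standard error = √((0.07 + 0.02) / 288) = 0.0177
- Power = Φ(0.05 / 0.0177 − 1.96) = 80.7%; detectable difference about 49/1000/year

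Section 9.2.3 therefore reproduces, with the first-year MDA rate and one year of person-time.

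**2. Length of the post-intervention series.** If a 3-year study starting in the first semester of 2018 closes between January and mid-2021, and the malaria posts keep reporting:

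| Villages | Start | Years after intervention |
|---|---|---|
| MDA, earliest dated | January 2015 | 6.0 to 6.5 |
| MDA, latest dated | April 2016 | 4.7 to 5.2 |
| MSAT | 2018 onward | 1 to 3 (section 7.9) |

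The MDA dates cover 40 of the 60 villages counted in 9.2.3.

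**3. Size of the second-year rise.** Five of 52 hotspots above 50/1000 in one month, each hotspot weighted equally and the figure read as cases per 1000 inhabitants in that month, contribute at least 5 × 50 / 52 = 4.8/1000 to the second-year average. Against the first-year rate this is 4.8 / 20 = 24%. Spread over five years with every other year at 20 (an assumption), the mean is (5 × 20 + 4.8) / 5 = 21.0/1000/year.

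**4. Sensitivity of the sizing.** The whole-series MDA rate is not in the documents. Using the formula in step 1, with MSAT held at 70 and the effective number at 288:

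| Assumed MDA rate per 1000/year | Difference from 70 | Power |
|---|---|---|
| 10 | 60 | 95% |
| 15 | 55 | 89% |
| 20 | 50 | 81% |
| 25 | 45 | 70% |
| 30 | 40 | 57% |

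The stated 80% thus belongs to the first-year MDA rate. This table varies the rate only; it does not model longer person-time.

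**5. Later MSAT in MDA villages.** Section 9.2.3 removes villages that receive MSAT after MDA from the MSAT group. It does not say that their time after MSAT is cut from the MDA series. For the 40 dated villages, the first 12 months after MDA end by about April 2017, before any MSAT, so a first-year window avoids the problem there.

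**The case against.** The strongest reply is that the documents contain no two competing outcome definitions. Section 9.2.3 uses the first-year MDA rate as a planning input and does not define a window. That is correct, and a reader who infers a flat contradiction between section 4 and 9.2.3 goes too far.

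The reply continues that the whole series may simply be the data for an adjusted model. Section 4 gives the primary outcome a similarly long window, and 9.1 mentions adjusted estimates from all available malaria post follow-up. That is possible, but the sentence in 9.1 breaks off in the text available. The model in 9.3 has a single 0-1 MSAT term and a 12-month window on each side, and it is not extended to MDA. Nothing readable equalises time since intervention between the two groups.

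Third, the documented late effect is small over a long series. The rise did not persist, and on the arithmetic above it moves a five-year MDA mean only from 20 to about 21. If MDA incidence kept falling, power would increase. Both points stand. They show that the direction and size of the distortion are unknown, not that it is absent, and they do not touch the outcome-dependent follow-up in the MSAT villages.

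Fourth, 12 months before intervention is an imperfect baseline. Group 1 is selected on incidence in that same period (sections 5 and 7.1), while MDA hotspots were selected on prevalence (section 3), so regression to the mean would favour MSAT. This stands, and the fix has to make it visible. In addition, the Figure 1 legend gives a median of 12 months of malaria post activity before intervention (IQR 5 to 16). If that describes the MDA villages, about half lack a full year.

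**Conclusion.** The point holds in a limited form. The tertiary incidence contrast has a stated window that mixes unequal periods, a sizing based on first-year MDA incidence, and no incidence analysis in 9.3 to reconcile them. The imbalance is about 4.7 to 6.5 years for the dated MDA villages against 1 to 3 years for MSAT, given a 3-year study from 2018 and continued reporting. The one late effect the documents allow to be sized is at least 4.8/1000 in the second year after MDA, about 24% of the first-year rate.

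Three stronger readings are not supported:

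- A uniform five years against one is stated nowhere; one year is only the MSAT minimum.
- A reader might infer that several MDA years would be summed against one MSAT year and reverse the ranking. Sections 9.1 and 9.2.3 work in rates per year, so that does not follow.
- A reader might infer that early malaria post years inflate the MSAT baseline by a calculable amount. The documents give no rate of decline for these villages, and section 3 reports slower or no decrease where asymptomatic prevalence is high.

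The objective is tertiary. Neither the primary result nor the primary sample size is affected. The change should be made, but the trial does not depend on it.

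**What to change.** In section 4 and in 9.3, define the formal tertiary incidence contrast as the annualised rate in the first 12 months after the first MDA or first MSAT, in both groups, relative to the 12 months before where available. This is the window behind the MDA rate in 9.2.3 and the one 9.3 uses for the primary outcome. Where a malaria post was open for less than 12 months beforehand, compare matched calendar months before and after in that village, and report how many villages this concerns in each group. State the time origin as well, because section 3 describes MDA as a 3-month campaign and MSAT as about one week.

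Add to 9.3 the incidence model for this comparison, which is now absent. Report the whole series as a descriptive or sensitivity analysis by months since intervention, before and after, with repeat MSAT and any MSAT in MDA villages marked. The pre-intervention part of that display also shows any regression to the mean from selecting group 1 on the prior 12 months.

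The cost is wording in two sections. No new data are needed and the sizing in 9.2.3 stands. The small downside is that later MDA follow-up does not enter the formal contrast.
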